### 9.6.9 Sample Size and Power Considerations

A sample size of 20 subjects is planned for this study. The primary efficacy endpoint, the proportion of subjects achieving and maintaining sUA <6 mg/dL for at least 80% of the time during Month 6, will be demonstrated to be statistically greater than 43.5% (proportion of responders during Month 6 in the Phase 3 studies), if at least 14/20 (70%) responders are observed. In that case, the lower bound of a 95% confidence interval for the proportion of responders will be about 46%.

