### 10.2 Primary Efficacy Endpoint and Analysis

The primary efficacy endpoint is the proportion of Month 6 (Weeks 20, 21, 22, 23 and 24) responders, defined as subjects achieving and maintaining sUA <6 mg/dL for at least 80% of the time during Month 6.

The sUA concentrations vs. time (collected to the nearest minute in the CRF) curve will be used to estimate the proportion of time that the sUA is < 6 mg/dl using the available pre-infusion, non-infusion (if available), and post-infusion samples with non-missing sUA values.

The Month 6 period will include pre-infusion and post-infusion results at Week 20, results at Week 21, pre-infusion and post-infusion results at Week 22, results at Week 23, and results at Week 24 processed by the central laboratory. Central laboratory results from visits at which an infusion was not performed (e.g. subject discontinued pegloticase but remained in study or unscheduled visits) will be used when available. Section 10.1 shows the rules for inclusion of sUA values reported by local laboratories.

There will be no imputation of sUA values due to missed collections among those collected between Week 20 and Week 24. Only observed values will be included in the calculation. If central lab results are available, central lab results are used. If central lab results aren't available, local lab results will be used.

This document is confidential.

[REDACTED]

[REDACTED]

[REDACTED]

[REDACTED]

Results from visits where an infusion was not performed (e.g. subject discontinued pegloticase but remained in study) will be used when available. The only exception to this approach is for subjects meeting the stopping rule. Subjects meeting the stopping rule prior to Week 24 will be counted as non-responders. If only one sUA result is collected during the Month 6 period, response will be based on the single value being strictly < 6 mg/dL.

For subjects who postponed or missed visits due to COVID-19, only visits occurring prior to any disruption of treatment (> 21 days between infusions) or cessation in treatment will be used for the primary analysis. Any results following the disruption in treatment will be set to missing. Subjects with disrupted treatment due to COVID-19 at any point prior to the Month 6 period will not be included in the primary analysis.

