The proportion of hours during the period during which the sUA was less than 6 mg/dL will be summarized using descriptive statistics. If a subject has  $\leq 1$  data point in the period, then the proportion of hours will not be calculated. The number and proportion of subjects that discontinued treatment due to the stopping rule will be summarized. The number and proportion of responders will be summarized along with a 95% exact (Clopper-Pearson) CI for the proportion. In addition, the number and proportion of subjects missing all data in analysis period, subjects with only one measurement (above cutoff) in analysis period, and subjects with only one measurement (below cutoff) in analysis period will be summarized.

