#### Sensitivity Analysis for the Primary Endpoint

The primary efficacy analysis will be repeated for the ITT Population to (1) include all sUA results (if available) in the response calculation following discontinuation of treatment for subjects who meet stopping rule and continue in the study (2) include all sUA results corresponding to the Month 6 primary analysis period (if available) in the response calculation following any COVID-19-related missing sUA assessments or disruption in treatment (excluding the first pre-infusion sUA after return from COVID-19-related pause in treatment).

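### On its natural reading, SAP 10.2 drops stopping-rule failures from the proportion-of-hours summary while counting them as non-responders, so that summary is biased upward

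*SAP*

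**What the plan says.** The primary endpoint (SAP 5.1 and 10.2) is the proportion of subjects with sUA below 6 mg/dL for at least 80% of Month 6. SAP 10.2 also plans a companion measure: "The proportion of hours during the period during which the sUA was less than 6 mg/dL will be summarized using descriptive statistics". For a subject with no more than one "data point in the period, then the proportion of hours will not be calculated".

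Three further statements decide who contributes to it:

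- Off-infusion results: "Results from visits where an infusion was not performed (e.g. subject discontinued pegloticase but remained in study) will be used when available".
- The next sentence limits this: "The only exception to this approach is for subjects meeting the stopping rule". It is followed by "Subjects meeting the stopping rule prior to Week 24 will be counted as non-responders".
- Sensitivity analysis (1) will "include all sUA results (if available) in the response calculation following discontinuation of treatment for subjects who meet stopping rule" and continue in the study.

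SAP 10.3.1 applies the same methods to the 5 mg/dL threshold. SAP 10.2 also reports how many subjects stopped by the rule, how many have no Month 6 data, and how many have a single value above or below the cutoff.

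**The concern.** One section treats the same subjects in two ways. In the responder count a stopping-rule subject is a failure, whatever is measured later. In the hours summary that subject may have no value at all, and no visible rule assigns one. The reason for absence is the outcome itself, two consecutive pre-infusion values above 6 mg/dL, so the loss is informative and pushes the mean upward.

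At stake is how a descriptive figure printed next to the primary result will be read. If failures are absent, it describes control among subjects who mostly did not fail, whereas the objective concerns everyone dosed. It could sit near its ceiling in a trial with few responders as easily as in one with many.

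**Working it through.** **The plan's own figure.** Protocol 9.6.9 says the responder proportion "will be demonstrated to be statistically greater than 43.5"% with at least 14 of 20 responders, and gives a lower 95% bound of about 46%. The two-sided exact (Clopper-Pearson) interval for 14/20 is 45.7% to 88.1%, which agrees. For 13/20 the lower bound is 40.8%, so 14 is the smallest count that clears 43.5%. Nothing below alters this, because the hours summary does not enter it.

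**Usable Month 6 values.** SAP 10.2 sets the sampling: "The Month 6 period will include pre-infusion and post-infusion results at Week 20, results at Week 21, pre-infusion and post-infusion results at Week 22", then Weeks 23 and 24. That is 7 values on infusion, or 5 without post-infusion samples. The rule counts from Week 2, so it can first be met at Week 4. The infusion visits from Week 4 to Week 22 give 10 possible trigger visits.

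| Rule met at | Reading A: values after stopping not used | Reading B: values kept, only response overridden, all visits attended |
|---|---|---|
| Weeks 4 to 18 (8 visits) | 0 | 5 |
| Week 20 | 1 (pre-infusion) | 5 |
| Week 22 | 4 (Week 20 pre and post, Week 21, Week 22 pre) | 6 |

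Under A, 9 of the 10 trigger visits leave at most one value, so no hours figure. Under B, none do. Nine of ten visits is not the same as 90% of failures, because the documents do not say when failures occur.

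**Which reading.** The approach to which stopping-rule subjects are the exception is the use of off-infusion results. Sensitivity analysis (1) puts those results back, which makes sense only if the primary response calculation leaves them out. That favours A. The text does not explicitly extend the exception to the hours summary.

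**Size (assumptions, not document figures).** Let R responders average r of the time below 6 mg/dL, let F = 20 − R all be stopping-rule failures averaging f, and let k of them have a calculable value.

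- All subjects: M_all = (R·r + F·f)/20
- As reported: M_k = (R·r + k·f)/(R + k)
- Shift = M_k − M_all. With k = 0 it equals (F/20)(r − f).

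With r = 0.95:

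| R, F | k | f = 0% | f = 25% | f = 50% |
|---|---|---|---|---|
| 14, 6 | 0 | 95.0 − 66.5 = 28.5 points | 95.0 − 74.0 = 21.0 | 95.0 − 81.5 = 13.5 |
| 14, 6 | 3 | 11.7 | 8.6 | 5.6 |
| 14, 6 | 6 | 0 | 0 | 0 |
| 9, 11 | 0 | 52.2 | 38.5 | 24.7 |

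For 14 responders and k = 0, r = 0.90 gives 12 to 27 points and r = 1.00 gives 15 to 30. With every failure excluded, the reported mean is 95% at both 14/20 and 9/20 responders.

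**The case against.** The strongest reply is that the one-value rule alone removes almost nobody. The protocol keeps stopped subjects on study and seeks their sUA at Weeks 20 to 24 (urged in 9.3.3.1.1, required in 9.5.7.3), which is five scheduled values each. The sentence after the exception concerns response classification, and sensitivity analysis (1) refers to the response calculation; neither mentions hours. Redacted lines stand just before these sentences in SAP 10.2 and may hold further rules. This stands in part: exclusion depends on how far the exception reaches, or on missed visits, and under Reading B with full attendance the shift is zero. But the SAP leaves the point open, and its wording favours exclusion.

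It is also fair that the measure is descriptive, that n is required for continuous summaries (SAP 8.1), and that exclusion counts are reported. These would alert a careful reader, but they do not supply an all-subject figure. It is also unclear whether a stopped subject who attended Weeks 20 to 24 would be counted as missing all data.

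A reader might infer that the summary describes only responders. It does not. Week 22 triggers, on-treatment subjects below 80% of the time, and subjects who stopped for other reasons but have values all remain. Conversely, a subject with a single value below 6 mg/dL is classed as a responder (unless the stopping rule was met) yet has no hours figure.

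Finally, assigning 0% overrides observed data. If failures truly average 25% to 50%, it understates the all-subject mean by 0.3 × 25 = 7.5 to 0.3 × 50 = 15 points with 6 failures. That is a good reason to show both versions.

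**Conclusion.** The concern holds in a limited form. On the natural reading of SAP 10.2, subjects stopped at or before Week 20 are failures in the responder count and absent from the hours summary, which is then biased upward relative to the ITT objective.

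The size cannot be derived, since neither the number of stopping-rule failures nor their off-drug sUA is given. The illustrative range is 0 points (post-stopping values used, full attendance) to about 13 to 29 points (6 of 20 failures, all excluded, responders at 95%, failures at 0% to 50%).

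A reader might infer that the primary result is compromised, or might set this shift against the planned gain over 43.5%. The documents support neither. The responder proportion, its exact interval and the 14/20 benchmark are unaffected, and mean hours and responder rate are different quantities. This is a flaw in a descriptive summary that should be corrected.

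**What to change.** In SAP 10.2, carried through to the 5 mg/dL analysis in 10.3.1:

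1. State whether sUA collected after the stopping rule is met enters the proportion-of-hours summary.
2. Present the summary for all subjects in the primary analysis, with 0% for those counted as non-responders by the stopping rule or by withdrawal from treatment without the planned sUA (Protocol 9.6.5.1). Show the number assigned 0%.
3. Beside it, give a version using these subjects' observed Month 6 values where available.
4. Keep the available-case summary as a row labelled as such, with its n.

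The cost is a few SAP sentences, one derived value per failing subject and extra table rows; no new data are needed. The mean will look less favourable and the distribution will have two peaks, so report the median and range with it. The 0% version is a conservative bound: observed time below the threshold may be above 0%, and may reflect oral urate-lowering therapy, which Protocol 9.3.3.1.1 allows to resume once the End of Pegloticase Visit laboratory samples are taken.

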#### Sensitivity Analysis for the Primary Endpoint

The primary efficacy analysis will be repeated for the ITT Population to (1) include all sUA results (if available) in the response calculation following discontinuation of treatment for subjects who meet stopping rule and continue in the study (2) include all sUA results corresponding to the Month 6 primary analysis period (if available) in the response calculation following any COVID-19-related missing sUA assessments or disruption in treatment (excluding the first pre-infusion sUA after return from COVID-19-related pause in treatment).

### **10.3. Secondary Efficacy Endpoints and Analyses**

Observed efficacy endpoints will be summarized by pegloticase treatment status (On Treatment, Post-Treatment, and Overall), visit, and treatment group. On Treatment will include post-baseline visits on or after pegloticase infusions. Subjects will only be summarized in the On Treatment visits for visits that occur (and results available) while still receiving pegloticase infusions. End of pegloticase infusion visit (windowed) if one occurs, will also be considered On Treatment, as will the Week 24 visit for subjects who complete treatment and study at Week 24. Post-Treatment visits are any post-baseline visits after the end of pegloticase infusions (or Week 24/EOS if subjects complete treatment). Overall status will include all visits for all subjects regardless of pegloticase treatment status.

This document is confidential.

For subjects who postponed or missed visits due to COVID-19, only visits occurring prior to any disruption of treatment (> 21 days between infusions) or cessation in treatment will be used for the analysis summaries. Any results following the disruption in treatment will be set to missing. Subjects with disrupted treatment due to COVID-19 at any point prior to the Month 6 analysis period will not be included in the responder analysis.

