#### **8.3.3.** Missing Data due to COVID-19

No imputation of missing data will be done for subjects who miss assessments or postpone assessments due to COVID-19. Only the observed data will be used in data summaries, when indicated.

Additional details of how the missing data will be handled in analysis are provided in sections 10.2, 10.3 and 10.4 for each endpoint.

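### For subjects with COVID-19-affected visits, SAP 10.3 drops observed HAQ results from a summary it defines as covering all visits, and no HAQ analysis puts them back

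*SAP*

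**What the plan says.** SAP 10.3 summarises observed secondary efficacy endpoints by treatment status: *On Treatment*, *Post-Treatment* and *Overall*. It defines the last of these without qualification: "Overall status will include all visits for all subjects regardless of pegloticase treatment status".

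The next paragraph covers subjects who postponed or missed visits because of COVID-19. For them, "only visits occurring prior to any disruption of treatment (> 21 days between infusions) or cessation in treatment will be used" in the summaries, and a further sentence sets results after the disruption to missing. Neither sentence mentions *Overall*, and no cause is attached to cessation.

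SAP 10.3.2 and 10.3.3 present HAQ pain and HAQ-DI by *On Treatment* and *Overall*, so both rules act on the same tables. SAP 5.2 makes the change to Week 24 in each score a secondary endpoint; these are two of the three.

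SAP 8.3.3 rules out imputation for COVID-19 and adds: "Only the observed data will be used in data summaries, when indicated". It leaves the detail to Sections 10.2 to 10.4. The sensitivity analysis sits under the primary endpoint: "The primary efficacy analysis will be repeated for the ITT Population". Both of its variants bring back serum uric acid (sUA) results only.

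Protocol 9.6.5.1 says only that subjects affected by the pandemic may receive special consideration. SAP Section 14 does not list the truncation among the changes from the protocol.

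**The concern.** Taken literally, a summary of all visits for all subjects cannot also omit collected visits from some of them. Two programmers could produce different Week 24 HAQ tables and both claim to follow the SAP.

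If the second paragraph prevails, two things are at stake. First, the label *Overall* no longer describes the estimate, and nothing visible in the SAP gives a HAQ result on all observed data. Second, whether a HAQ value after stopping is kept depends on whether the subject ever postponed a visit for COVID-19. Protocol 9.3.3.1.1 especially encourages subjects who stop infusions to attend Weeks 20 to 24 so that key assessments can be made. For the affected subjects, the SAP would then leave out the Week 24 HAQ collected there.

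**Working it through.** **1. The plan's own design figure.** Protocol 9.6.9 states: "A sample size of 20 subjects is planned for this study". The primary proportion "will be demonstrated to be statistically greater than 43.5"% "if at least 14/20 (70%) responders are observed", and then "the lower bound of a 95% confidence interval for the proportion of responders will be about 46"%. The exact (Clopper-Pearson) 95% interval for 14/20 is 45.7% to 88.1%, so the figure reproduces. At 13/20 the lower bound is 40.8%, so 14 is the smallest qualifying count. This concerns the primary endpoint. The documents state no precision or power for HAQ; only the planned n = 20 carries over.

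**2. How easily the rule is triggered.** Infusions are every 14 days and visits have a window of ±3 days (Protocol synopsis, study schematic).
- No infusion missed: longest gap = 14 + 3 + 3 = 20 days, not above 21.
- One infusion missed: gap = 28 − 6 to 28 + 6 = 22 to 34 days, always above 21.
- Week 22 missed: no later infusion exists to close a gap, so the cessation clause does the removing.

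**3. Which HAQ visits go.** Post-baseline HAQ visits are Weeks 6, 14, 20 and 24 and the 3-month follow-up (SAP 10.3.2, 10.3.3). Counting everything after the last infusion before the gap as removed:

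| Infusion missed | HAQ visits removed (of 5) | Week 24 removed? |
|---|---|---|
| Weeks 2 to 6 | 5 | yes |
| Weeks 8 to 14 | 4 | yes |
| Weeks 16 to 20 | 3 | yes |
| Week 22 | 2 | yes |

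If the disruption is instead dated from day 22 after the last infusion, a HAQ taken in the same week as the missed infusion (Week 6, 14 or 20) survives. Week 24 is still removed in every row. Resuming and completing treatment does not bring it back.

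**4. The same stop under both rules.** Take subjects who attend Week 24:

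| Subject | Week 24 HAQ in *Overall* |
|---|---|
| Stops for lack of efficacy, no COVID-19 visit problem | kept |
| Same stop, but one earlier visit postponed for COVID-19 | dropped (cessation clause) |
| Gap above 21 days for another reason, then resumes | kept |
| Gap above 21 days with visits missed for COVID-19, then resumes | dropped (disruption clause) |

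**5. Precision at Week 24.** The number affected, k, is not in the documents; k = 1 to 6 is an assumption, with no replacement and an unchanged SD. Half-width in SD units = t(0.975, n − 1)/√n, with n = 20 − k.

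| k | n | Half-width (SD) | Ratio to n = 20 |
|---|---|---|---|
| 0 | 20 | 0.468 | 1.000 |
| 1 | 19 | 0.482 | 1.030 |
| 3 | 17 | 0.514 | 1.099 |
| 5 | 15 | 0.554 | 1.183 |
| 6 | 14 | 0.577 | 1.234 |

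If the SAP's normal-theory interval means a normal quantile rather than t, the ratio is √(20/n): √(20/19) = 1.026 and √(20/14) = 1.195 at the two ends.

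**6. Shift in the mean.** Shift = d × k/20, where d is the difference in mean change between kept and dropped subjects. The documents give no d. As an assumption on the 0 to 100 pain scale, d = 10 gives 10 × 3/20 = 1.5 points (k = 3) or 10 × 5/20 = 2.5 (k = 5). With d = 20 these double to 3 and 5. With d = 0 there is no shift.

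**The case against.** The strongest reply is that this is a general rule followed by a specific one. *Overall* says which treatment phases are pooled; the COVID-19 paragraph says which visits of a defined group enter any summary. A programmer can apply the second and then the first. SAP 10.2 applies the same truncation to the primary endpoint, so it looks deliberate, and SAP 8.3.3 defers to these sections and so creates no conflict of its own. Excluding values after an externally imposed dosing gap is a legitimate pre-specified choice. HAQ is descriptive, with no formal testing (Protocol 9.6.5), and the values still appear in listings (SAP 8.1).

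Much of that stands: the reading is workable and truncation is not wrong in itself. But under it *Overall* is mislabelled, no all-observed HAQ estimate remains, and the cessation clause still treats otherwise identical stoppers differently. COVID-19-caused cessation may be what was meant, but the text does not say so.

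Four stronger inferences are not supported:
- That all HAQ after stopping is discarded. The rule reaches only subjects who postponed or missed visits for COVID-19, and the set-to-missing sentence names only the disruption.
- That the mean is pulled towards successful subjects in general. COVID-19 scheduling is not defined by HAQ outcome; only the cessation clause ties deletion to treatment failure.
- That no secondary endpoint has a sensitivity analysis. The 5 mg/dL responder endpoint may inherit the primary one, because SAP 10.3.1 adopts the Section 10.2 methods.
- That the wider intervals are expected effects. The count is unknown, and Protocol 9.3.4.1 allows COVID-19-affected subjects to be replaced at the sponsor's discretion.

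The absence of a HAQ sensitivity analysis is shown for the visible SAP; the table index named in its contents list is not in the available text.

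**Conclusion.** The point holds in limited form. SAP 10.3 gives *Overall* a definition that its next paragraph overrides for COVID-19-affected subjects without saying so. For HAQ pain and HAQ-DI this removes observed data, always including Week 24 after one missed infusion, and the visible SAP has no HAQ analysis that restores them.

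The certain part is textual: the inconsistency, the low trigger and the missing HAQ counterpart to the sUA sensitivity analysis. The bias risk is specific to the cessation clause. The size is conditional. With 1 to 6 of 20 affected and none replaced, the t-based Week 24 interval is about 3% to 23% wider (10% for 3 subjects, 18% for 5). Any shift in the mean depends wholly on an assumed difference between dropped and kept subjects. Nothing here touches the primary success criterion.

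**What to change.** In SAP 10.3:
- apply the COVID-19 truncation to the *On Treatment* HAQ summary only;
- limit cessation in that rule to cessation caused by COVID-19;
- state that the *Overall* HAQ summary keeps every observed value, including those after a COVID-19 gap or after stopping.

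If the sponsor prefers to keep the truncation in *Overall*, say so in the definition and add an all-observed HAQ sensitivity summary parallel to the second variant of the primary endpoint's sensitivity analysis.

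The preferred change takes about two sentences and needs no new data. The cost is that *Overall* will include some time off drug, as it already does for every other early stopper; the *On Treatment* summary remains for readers who want that excluded.

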#### 10.3.1. Proportion of 5 mg/dL Responders during Month 6 (Weeks 20, 21, 22, 23 and 24)

The proportion of responders is defined as subjects achieving and maintaining sUA < 5 mg/dL for at least 80% of the time during Month 6. These will be calculated using the same method described for the primary efficacy endpoint ([Section 10.2](#)). The endpoints will be analyzed using the same methodology described in [Section 10.2](#).

